### **10.7.2 Unblinding**

At the initiation of the study, study site personnel will be instructed on the method for breaking the blind. The unblinding method will be either manual or electronic.

Unblinding of the individual subject's treatment by the investigator will be limited to medical emergencies or urgent clinical situations in which knowledge of the subject's study treatment is necessary for clinical management. In such cases, investigators will use their best judgment as to whether to unblind without first attempting to contact the medical monitor to discuss unblinding. If investigators deem it unnecessary to unblind immediately, they will first attempt to contact the medical monitor to discuss unblinding. If investigators have tried but are unable to reach the medical monitor, they will use their best judgment, based on the nature and urgency of the clinical situation, and may proceed with unblinding.

Contact information for the medical monitor (or appropriate backup) will be in a separate document.

If a subject's treatment assignment has been unblinded for a medical emergency or urgent clinical situation, the medical monitor will be notified within 24 hours of the unblinding event. The reason and the date of the unblinding will be documented clearly in the subject's study file. Information about the treatment assignment obtained from the unblinding will be maintained in a secure location with controlled access and will not be shared with Vertex, the CRO, or any site personnel (other than the physician treating the subject). In addition, the investigator will consider whether the clinical event that prompted unblinding will be considered an SAE, according to the regulatory definitions or criteria for SAEs, and if so, submit an SAE report to Vertex GPS or designee, per Section 13.1.2.

Vertex GPS or designee will also unblind any SAE reports in compliance with regulatory reporting requirements. In addition, Vertex may, for matters relating to safety, unblind individual subjects at any time.

## 11 ASSESSMENTS

The schedule of assessments is shown in [Table 3-1](#) and [Table 3-2](#).

### 11.1 Subject and Disease Characteristics

Subject and disease characteristics include the following: demographics, medical history, height, and weight.

Medical history will be elicited from each subject and extracted from medical records during screening. Based on the medical history, the subject will be assessed for any disqualifying medical conditions as specified in the inclusion and exclusion criteria. The medical history will include a complete review of systems, medical and surgical histories, and any allergies.

Height and weight will be measured with shoes off. Height will be collected at screening for all subjects. Following screening, height will be collected only for subjects  $\leq 21$  years of age on the date of informed consent.

### 11.2 Pharmacokinetics

#### 11.2.1 Blood Sampling

Blood samples will be collected to determine plasma concentrations of VX-121, TEZ, D-IVA, ELX, IVA, and relevant metabolites. These samples may also be used for further evaluation of the bioanalytical method, or for exploratory analyses that provide information on the metabolic pathways used by or affected by any study drugs.

For PK sampling at the Week 8 Visit, all subjects  $< 18$  years of age on the date of informed consent will have 1 postdose sample taken at 4 hours after the morning clinic dose. Approximately 40 subjects  $\geq 18$  years of age on the date of informed consent will have a total of 4 postdose samples taken at 4, 5, 6, and 7 hours after the morning clinic dose. All other subjects  $\geq 18$  years of age on the date of informed consent will have 1 postdose sample taken at 2 hours after the morning clinic dose. Vertex will manage the allocation of the 40 subjects providing more intensive PK sampling across study sites. If study drug is not administered at the Week 8 visit (i.e., due to study drug interruption or permanent discontinuation), a single PK blood sample will be collected at the visit.

All efforts will be made to obtain the PK samples at the exact nominal time relative to dosing. Acceptable windows for sampling times are shown in [Table 11-1](#). Samples collected outside of these acceptable windows will be considered protocol deviations. The exact time of the sample collection will be noted.

**Table 11-1 Acceptable Pharmacokinetic Sampling Windows**

Sampling Time	Time From Scheduled Sampling Allowed
Predose	-60 minutes
From 2 up to $\leq 7$ hours after study drug dosing	$\pm 15$ minutes

Blood samples will be collected as shown in [Table 3-2](#).

For each visit with a PK blood draw, a record of study drug administration will be collected as described in Section 9.6. The collection date and exact time that each PK blood sample is drawn will also be recorded.

Samples from the PK sampling will be kept frozen by Vertex or its designee until all analyses have been completed and then disposed of according to Vertex or designee standard operating procedures.

### **11.2.2 Processing and Handling of Pharmacokinetic Samples**

Detailed procedures for the collection of blood samples and further procedures for processing and handling of samples for PK analysis will be in the PK Sample Handling Guidelines.

### **11.2.3 Bioanalysis**

Samples will be analyzed using a validated analytical method in compliance with Vertex or designee standard operating procedures. A description of the assay and validation data will be provided in separate reports.

### **11.3 Pharmacodynamics**

While SwCl is a pharmacodynamic measure of CFTR function, it is also a measure of efficacy and is discussed in Section 11.5.2.

### **11.4 Exploratory Assessments**

These data will be used for internal exploratory purposes. Detailed procedures for the collection of blood samples and additional procedures for processing and handling samples for pharmacogenomics analysis will be provided in a separate document.

#### **11.4.1 Pharmacogenomics**

An optional single blood sample (DNA Sample) will be collected for potential exploratory evaluation of associations between DNA markers with PK, pharmacodynamics (PD), treatment response, AEs, and health and disease, especially CF, for subjects who choose to participate in this assessment (if permitted by local regulations).

#### **11.4.2 Inflammatory Mediators**

Blood samples (inflammatory mediator samples) will be collected at the time points noted in Table 3-2 and tested to assess markers related to inflammation. These may include, but are not limited to, C-reactive protein (CRP), immunoglobulin G (IgG), white blood cell (WBC, leukocyte) count, and interleukin-8 (IL-8). Specific instructions for the collection, processing, storage, and shipment of inflammatory mediator samples will be provided in the Laboratory Manual.

#### **11.4.3 Other Blood Biomarkers**

Additional blood samples for plasma and serum will be collected and banked for potential future exploratory evaluation of other blood biomarkers (e.g., proteins, peptides, lipids, metabolites, etc.) in relation to PK, PD, treatment response, AEs, and various disease manifestations of CF.

Optional blood samples (RNA Sample) may be collected (if permitted by local regulations) for potential exploratory evaluation of associations between RNA markers with PK, PD, treatment response, and AEs.

#### **11.4.4 Microbiology and Other Sputum Biomarkers**

Sputum samples will be collected at the time points noted in [Table 3-2](#) from subjects who can produce a sample spontaneously. Each sample will be processed and frozen for potential exploratory evaluation of microbiology analysis and sputum biomarkers (which may include, but are not limited to, qualitative and quantitative bacterial and viral assessments including genomic analyses, analysis of immune cells, inflammatory markers, proteins, peptides, lipids, and endogenous metabolites) in relation to PK, PD, treatment response, AEs, and various disease manifestations of CF.

Specific instructions for the collection, processing, aliquoting, storage, and shipment of sputum samples will be provided in the Laboratory Manual.

#### **11.4.5 Treatment Satisfaction Questionnaire for Medication**

The TSQM is a widely used generic measure of satisfaction with medication. The domains of the TSQM measure effectiveness, side effects, convenience, and global satisfaction. Because treatment satisfaction is not measured with the other health-related quality-of-life measures in this study, the TSQM will be included as an assessment for this purpose. Translations of the TSQM will be provided for participating centers with non-English-speaking populations.

All subjects should be instructed to complete the TSQM questionnaire on the Day -28 Visit based on their experience of their current medication regimen over the prior 2 to 3 weeks. Only subjects <18 years of age on the date of informed consent will complete the TSQM at subsequent visits; these subjects should be instructed to complete the TSQM based on their experience of the study drug over the prior 2 to 3 weeks. Subjects who discontinue study drug prematurely or who have interrupted study drug will still complete the TSQM basing their experience of the study drug if taken during the prior 2 to 3 weeks. If study drug was not taken during this period, the responses should be based on their experience of their current medication regimen.

TSQM may be completed within 5 days prior to the study visit. All questionnaires completed on the day of the study visit must be completed prior to any other assessments, with CFQ-R completed first.

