**Table 3-2 Study VX20-121-102: Run-in Period, Treatment Period, and Safety Follow-up Visit**

Event/Assessment a	Run-in Period		Treatment Period b						ETT Visit c	Safety Follow-up Visit 28 (± 7) Days After the Last Dose of Study Drug (If Applicable) d	Comments
	Day -28 (± 1 Day)	Day -14 (Day -15 to Day -3)	Day 1	Day 15 (± 3 Days)	Weeks 4, 8, 12, 16 (± 5 Days)	Weeks 20, 28, 32, 40, 44, 48 (± 5 Days)	Weeks 24 and 36 (± 5 Days)	Week 52 (± 5 Days)			
TSQM	X		X					X	X		May be completed within 5 days prior to the study visit. All questionnaires completed on the day of the study visit must be completed prior to any other assessments, with CFQ-R completed first. All subjects will complete the TSQM at the Day -28 Visit; only subjects <18 years of age on the date of informed consent will complete the TSQM at subsequent visits (Section 11.4.5).
CF-IQ	X		X		Week 4		Week 24	X			May be completed within 5 days prior to the study visit. CF-IQ, PGIS, and PGIC must be completed on the same day, and CF-IQ must be performed before PGIS and PGIC (as applicable). All questionnaires completed on the day of the study visit must be completed prior to any other assessments, with CFQ-R completed first (Section 11.4.6).
PGIS	X		X		Week 4						
PGIC			X		Week 4						
Height and weight	X		X	X	Weeks 4, 8, 16		X	X	X	X	Measured with shoes off. Following screening, height will be collected only for subjects ≤21 years of age on the date of informed consent

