#### **9.1.5.2 Discontinuation During the Treatment Period**

Subjects who prematurely discontinue study drug treatment during the Treatment Period should continue to complete all scheduled study visits for assessments following completion of the ETT Visit (and Safety Follow-up Visit, if applicable), as detailed in Table 3-2.

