## 9.3 Rationale for Study Elements

### 9.3.1 Study Design

This Phase 3 study will assess the efficacy and safety of VX-121/TEZ/D-IVA therapy in F/MF subjects.

A randomized, double-blind, ELX/TEZ/IVA-controlled study design was selected to ascertain the effects of VX-121/TEZ/D-IVA while avoiding observer bias. ELX/TEZ/IVA is considered an appropriate active control since it is an approved standard of care for treatment of patients with at least one *F508del* allele in some regions.

A 4-week Run-in Period was incorporated into this study to establish a reliable on-treatment (ELX/TEZ/IVA) baseline for comparison during the Treatment Period.

A 52-week treatment duration was selected to characterize the safety and efficacy of VX-121/TEZ/D-IVA compared to ELX/TEZ/IVA. The primary endpoint is absolute change from baseline in ppFEV1 through Week 24. Based on prior experience with CFTR modulators, 24 weeks is adequate to compare the efficacy of VX-121/TEZ/D-IVA versus ELX/TEZ/IVA on the endpoints being evaluated.

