**Table 9-2 Prohibited Medications**

Medication	Timing of Restriction		Rationale
	Start of Restriction	End of Restriction	
Non-Vertex CFTR modulators (investigational or approved)	None allowed within 28 days or 5 terminal half-lives (whichever is longer) before screening	None allowed through completion of study participation	These agents may confound the results of this study.
Vertex CFTR modulators (investigational or approved), except for study drugs	None allowed from the first dose of ELX/TEZ/IVA on Day -28	None allowed until after the last dose of study drug	These agents may confound the results of this study.

D-IVA: deutivacaftor; ELX: elexacaftor; IVA: ivacaftor; TEZ: tezacaftor

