8.5.1 Analysis of TSQM Domains

TSQM is a widely used generic measure of satisfaction with medication and has been demonstrated to be a valid and reliable measure of satisfaction in patients with CF¹⁰. It consists of 14 items to form 4 domains: effectiveness (items 1, 2, 3), side effects (items 4, 5, 6, 7, 8), convenience (items 9, 10, 11), and global satisfaction (items 12, 13, 14). The score of each domain is a scaled score that ranges from 0 (least satisfied) to 100 (most satisfied). Scaled score for each domain can be calculated using the scale scoring algorithm¹¹.

Absolute change from baseline in TSQM domains at Week 52 (only for subjects aged ≥12 years to <18 years at the date of informed consent) will be analyzed descriptively.

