 - i. The measurement closest to the target day will be used; or
 - ii. If there are multiple measurements with the same distance from the target day, the latest measurement will be used. If the latest measurement cannot be determined, and there are both scheduled and unscheduled visits, then the unscheduled visit will be selected.

³ For measurements collected on the date of first dose of study drug in the Treatment Period, if it cannot be determined whether a measurement is before or after the first dose:

- a. Scheduled measurements will be treated as pre-dose observations.
- b. Unscheduled measurements will be treated as post-dose observations.

⁴ For safety assessments, the Safety Follow-up analysis visit will be based on the nominal Safety Follow-up visit. If a subject does not have a nominal Safety Follow-up visit but has an early termination of treatment (ETT) visit with study day >379, then the ETT visit will be mapped to the Safety Follow-up analysis visit.

⁵ For efficacy assessments, if a subject has a nominal Safety Follow-up visit with study day >379, then the nominal Safety Follow-up visit will be mapped to the Safety Follow-up analysis visit; else if a subject does not have a nominal Safety Follow-up visit with study day >379 but has an ETT visit with study day >379, then the ETT visit will be mapped to the Safety Follow-up analysis visit; else if there are multiple assessments with study day >379, then the earliest record will be selected as the Safety Follow-up analysis visit.

Derived Variables:

1. Age (in years) at first dose date and at nominal visits (for demographics, listings, and the calculation of [percent] predicted spirometry variables):

Obtain the age at informed consent (in days) in “yy, mm” format (e.g., 24 years, 6 months) from the Vital Signs (VS) page at the Screening Visit, and add 15.22 days to convert to days.

Obtain the informed consent date.

Table 11-1 Analysis Visit Windows for Safety and Efficacy Assessments

Assessment	Visit ¹	Target Study Day	Analysis Visit Window ^{2,3,4} (in study days)

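### The Week 52 TSQM summary for subjects under 18 mixes ratings of study drug with ratings of whatever regimen replaced it

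*Protocol*

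**What the plan says.** Protocol Table 3-2 schedules the TSQM at Day -28, Day 1, Week 52 and the ETT Visit. All subjects complete it at Day -28; after that, "only subjects <18 years of age on the date of informed consent will complete the TSQM at subsequent visits".

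What the form refers to depends on recent dosing. Under Protocol 11.4.5, subjects who discontinued or interrupted study drug "will still complete the TSQM basing their experience of the study drug if taken during the prior 2 to 3 weeks". For those who did not take it in that time the referent changes: "If study drug was not taken during this period, the responses should be based on their experience of their current medication regimen".

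Three other protocol provisions bear on who can be in that position at Week 52:
- Section 9.1.5.2: subjects who stop treatment early "should continue to complete all scheduled study visits for assessments following completion of the ETT Visit".
- Table 9-2, on other Vertex CFTR modulators, gives the end of the restriction as "None allowed until after the last dose of study drug".
- Section 9.3.1 says of ELX/TEZ/IVA that "it is an approved standard of care for treatment of patients with at least one" *F508del* allele, in some regions.

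SAP 8.5.1 plans "Absolute change from baseline in TSQM domains at Week 52", descriptively, for subjects aged 12 to under 18 at consent. SAP Appendix A gives the TSQM one post-baseline window, study days [1, 379] with target Day 365. If several records fall in the window, "The measurement closest to the target day will be used". Neither place separates, flags or excludes forms that rate something other than study drug.

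**The concern.** The TSQM asks how satisfied a person is with a medication. Its score has meaning only together with the product being rated. The protocol deliberately lets that product change once study drug has been out of use for 2 to 3 weeks. The SAP then treats all forms as the same variable.

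A reader of the Week 52 table will take the effectiveness, side-effects, convenience and global satisfaction scores as describing the drug named at the head of the column. For some subjects they would describe a different regimen. In the VX-121/TEZ/D-IVA column, that regimen could be the trial's comparator. Nothing in the planned output would show how many such ratings a column contains.

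**Working it through.** **No plan figure to reproduce.** The documents give no sample size, expected change or SD for the TSQM, no number of subjects under 18, and no share expected to be off drug at Week 52. The check is mainly one of text.

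**Step 1: can an off-drug rating exist at Week 52?** Yes. A subject who stops early stays in scheduled visits (Protocol 9.1.5.2), and Week 52 carries a TSQM (Table 3-2). If no study drug was taken in the prior 2 to 3 weeks, the form rates the current regimen (Protocol 11.4.5). The same holds for a long interruption, which 11.4.5 also covers.

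**Step 2: can the rated regimen be ELX/TEZ/IVA?** Yes, where it is available, because the Table 9-2 bar lifts after the last dose. Protocol 10 defines study drug in the Run-in Period as ELX/TEZ/IVA and IVA, so the Day 1 form of a subject who has just completed the run-in rates that regimen. A VX-121/TEZ/D-IVA subject who later moves to commercial ELX/TEZ/IVA would then contribute a change between two ratings of the comparator regimen.

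**Step 3: which form does the SAP keep?** Take an ETT form on the day shown, and a Week 52 form on Day 365:

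| ETT form on day | Inside [1, 379]? | Distance to Day 365 | Kept if a Day 365 form exists |
|---|---|---|---|
| 30 | yes | 335 | Day 365 form |
| 100 | yes | 265 | Day 365 form |
| 200 | yes | 165 | Day 365 form |
| 340 | yes | 25 | Day 365 form |

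The Day 365 form has distance 0 and always wins. If the subject does not attend Week 52, the ETT form, even from Day 30, becomes the Week 52 value. So for a subject who stopped early, attendance decides whether the Week 52 value rates another regimen late or, usually, study drug early.

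**Step 4: does any other rule resolve this?** The treatment policy strategy is stated for ppFEV1 (SAP 8.3.1.2) and carried to the key secondary sweat chloride endpoints (SAP 8.3.2.2). No estimand or intercurrent-event rule is given for the TSQM. Grouping by randomized arm is itself inferred, from SAP 7.2 and the listing of the TSQM under efficacy assessments in Appendix A; SAP 8.5.1 does not state it.

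**Step 5: illustrative size.** Shift in an arm mean = p × D, where p is the share of analysed subjects rating another regimen and D is the gap between that rating and the study-drug rating on the 0 to 100 scale. Both inputs are assumptions.

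| p | D = 5 | D = 10 | D = 20 |
|---|---|---|---|
| 2% | 0.1 | 0.2 | 0.4 |
| 5% | 0.25 | 0.5 | 1.0 |
| 10% | 0.5 | 1.0 | 2.0 |
| 15% | 0.75 | 1.5 | 3.0 |

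The difference between arms moves by the difference of the two products, so equal p and D in both arms would cancel.

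**The case against.** **Nothing inferential rests on the TSQM.** Protocol 11.4 places it among exploratory assessments for internal use. It is in no endpoint list and not in the testing hierarchy of SAP 8.3.2.3, and SAP 8.5.1 plans no model, interval or test. This stands, and it limits the point to the clarity of one descriptive table.

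**Keeping off-drug data in the randomized arm is the SAP's general habit.** That is true for ppFEV1 and sweat chloride, and it is a fair defence there: sweat chloride is the same variable on or off drug. It does not carry over to the TSQM, because after a switch the question itself refers to a different product.

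**Part of the extent is already visible.** SAP 8.2.1 tabulates discontinuations with reasons, and SAP 8.2.4 lists post-treatment medications. Neither is specific to subjects under 18 or linked to the TSQM form used.

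A reader might also infer more than the documents support:
- *That the replaced ratings come from dissatisfied subjects.* Protocol 9.8, 9.9 and 11.6.7.2 give many other reasons for stopping, including an unconfirmed genotype, pregnancy, liver-test stopping rules, noncompliance and administrative reasons.
- *That every displaced ETT form rated study drug.* Protocol 9.1.5 allows an ETT Visit 3 weeks or later after the last dose, and such a form may already rate the current regimen.
- *That the 10% drop-out planning figure gives the affected share.* It is an allowance at Week 24 for the power calculation. Subjects who leave the study supply no Week 52 form; the relevant group stops drug and still attends, and its size is not given.
- *That a treatment comparison is biased.* The SAP makes no formal one on the TSQM. For a control subject who moves to commercial ELX/TEZ/IVA, the active regimen does not change.

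**Conclusion.** The point holds, with low impact. Followed as written, the plan produces a Week 52 TSQM summary in which some values rate study drug and others rate a different regimen, with no way to tell them apart in the table. Where an ETT rating of study drug exists, a Week 52 rating of another regimen replaces it.

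The effect is confined to an exploratory, descriptive summary in subjects under 18. No primary, key secondary or other listed endpoint is touched. The size cannot be determined from the documents. The range of 0.1 to 3.0 points in an arm mean rests entirely on an assumed share of 2% to 15% and an assumed gap of 5 to 20 points; at 10% and 10 points it is 1.0. The case for a change rests on what the summary means rather than on those numbers.

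**What to change.** In SAP 8.5.1:
1. Classify each post-baseline TSQM from dosing records by whether any study drug was taken in the 21 days before the form was completed. Keying this to any dose, not only to the last dose, covers interruption as well as discontinuation. Use the completion date, since the form may be filled in up to 5 days before the visit.
2. Summarise Week 52 ratings of study drug by arm.
3. Present ratings of another regimen separately, labelled as such.
4. Show ETT ratings of study drug as their own row, and do not map them to Week 52. Amend the TSQM row in Appendix A to match; otherwise the [1, 379] window would turn an early ETT form into a Week 52 value.
5. Report the number of forms in each category by arm.

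The protocol's 2 to 3 weeks is not a single cut-off. Twenty-one days takes its upper end, so what was rated on forms completed 15 to 21 days after the last dose taken remains uncertain; the SAP should say so.

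The cost is a few sentences and a date check. SAP 8.2.5 and 8.2.6 already use last dose dates and days of interruption, so no new data are needed. The downside is that the Week 52 study-drug row covers only subjects still on drug, so it should be read alongside the ETT and off-drug rows.
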